9.2. Secondary Variables

Eye Tracking

Eye movements will be recorded by a human infrared eye tracking system (Tobii TX300) with 300 Hz temporal resolution. The target stimulus, which will be created in Toby Studio program, will be presented on a computer screen 40 cm from the subject, in a darkened room. Before testing, an eyechart will be used to verify that all subjects will have a normal or corrected-to-normal vision. Calibration based on 9 points, including center and peripheral, will be performed before each session, which also will ensured that all subjects will have a full range of oculomotor movement.

32 Channel – qEEG

Continuous qEEG recordings will be performed in both resting conditions and cognitive tasks, during the following sequences: 1) eyes open – 5 minutes; 2) eye close – 5 minutes; 3) cognitive tests – 20 minutes; 4) eyes open -5 minutes; 5) eyes closed - 5 minutes. Will be used scalp electrodes fixed in an elastic cap, located according to the international 10–10 system and electrode impedances will be keep below 5 k Ω . qEEG data will be recorded using 32 channels.

9.3. Further Variables

Neurological and physical examinations will be performed according to hospital standard procedures and will be recorded in the CRF.

Anamnestic data will be collected according to standard hospital procedures and the medical history will be documented in the CRF.

Vital signs including systolic and diastolic blood pressure, heart rate, respiratory rate and body temperature will be measured and documented in the CRF.

Standard laboratory parameters will be analysed according to standard procedures.

Information on all concomitant treatments and medications will be collected and documented.

Information on adverse events and patient safety will be collected in the CRF.

9.4. Source Documents

The following definitions of source documents shall apply:

Variable	Source document
Informed consent form (s)	Informed consent form

Page 32 of 58

Variable	Source document
Patient's data (e.g. demographics: sex, age, weight, indication, concomitant diseases, medication history etc.)	CRF
Medical History	CRF
Physical & Neurological Examination	CRF
Vital signs	CRF
Outcomes Variables	CRF
Laboratory Variables	CRF
qEEG	Electronic Patient File
ET	Electronic Patient File
Concomittant Medication	CRF
Adverse Events	CRF

10. ASSESSING AND REPORTING OF ADVERSE EVENTS

Throughout the course of the clinical study particular attention is paid to the Adverse Events and Adverse Drug Reactions mentioned below.

10.1. Adverse Events (AE)

A Serious/Adverse Event (S/AE) is any untoward medical occurrence in a patient or clinical investigation subject administered a pharmaceutical product and which does not necessarily have a causal relationship with this treatment. An AE can therefore be any unfavourable and unintended sign (including an abnormal laboratory finding), symptom, or disease temporally associated with the use of an Investigational Product, whether or not related.

10.2. Adverse Drug Reaction (ADR)

All untoward and unintended responses to an Investigational Product related to any application / dose administered. The phrase "responses to an Investigational Product" means having a reasonable causal relationship as judged by either the Investigator or the Sponsor. The expression

STUDY ID: CAPTAIN - rTMS

reasonable means to convey in general that there is evidence or argument to suggest a causal relationship.

Regarding marketed Investigational Products: a response to a product which is noxious and unintended and which occurs at applications normally used in man for prophylaxis, diagnosis, or therapy of diseases or for modification of physiological function.

10.2.1. Serious Adverse Event or Serious Adverse Reaction (SAE/SAR)

Serious Adverse Events will due to the underlying constitution of the patient be considered for AE documentation.Serious Adverse Drug Reactions will be dealt with as described below.

Expedited Reporting is required if the following criteria apply (ICH E2A):

- 1. Serious
- 2. Unexpected
- 3. Reasonable causal relationship to study treatment.

An Adverse Drug Reaction is considered serious if it:

- Results in Death
- Is life threatening
- Requires additional inpatient hospitalization or prolongation of existing hospitalization
- Results in persistent or significant disability / incapacity
- Results in a congenital anomaly or birth defect
- Other medically significant event that requires immediate medical or surgical intervention

Unexpected means:

• Not consistent with Investigators Brochure or SmPC

Causal Relationship means:

Date: 040418

STUDY ID: CAPTAIN - rTMS

- There are facts/evidence to suggest a causal relationship
- As judged by the reporting health care professional to have reasonable suspected causal relationship

NOTE

Death: is the outcome of an Adverse Event. The event to be reported comprehensively is the medical condition leading to death, e.g. underlying disease, accident.

Life-threatening: in the definition of a Serious Adverse Event or Adverse Reaction refers to an event in which the patient was at risk of death at the time of the event; it does not refer to an event which hypothetically might have caused death if it was more severe.

Medical judgement should be exercised in deciding whether an Adverse Event / Reaction is serious in other situations. Important Adverse Events / Reactions that are not immediately life-threatening or do not result in death or hospitalisation but may jeopardise the patient or may require intervention to prevent one of the other outcomes listed in the definition above, should also be considered serious.

10.3. Suspected Expected Serious Adverse Reaction (SESAR)

Any adverse reaction that is classed in nature as serious and which is consistent with the available information on the medicinal product in question set out in the SmPC

10.4. Suspected Unexpected Serious Adverse Reaction (SUSAR)

Any adverse reaction that is classed in nature as serious and which is **not** consistent with the available information on the medicinal product in question set out in the SmPC

10.5. Recording of Adverse Events

All adverse events, according to previously provided definitions, whether they are considered serious or not will be documented and were applicable reported.

The Investigator must report in detail all adverse signs and symptoms which are either volunteered by patients or observed during or following the course of Investigational Product administration on the appropriate CRF page.

Included in the description should be the nature of the sign or symptom; the date of onset; date of resolution (duration); the severity / intensity; the relationship to study treatment or other therapy; the action taken (if any), and the outcome.

10.5.1. Definition of Adverse Event intensity

Intensity	Definition
Mild	Patient is aware of signs and symptoms but they are easily tolerated
Moderate	Signs / symptoms cause sufficient discomfort to interfere with usual activities
Severe	Patient is incapable to work or perform usual activities

10.5.2. Definition of Adverse Event causality

On the basis of the WHO-UMC system for standardised case causality assessment (www.who-umc.org), the following categories are used to describe the degree of causality (all points should be reasonably complied with):

Definite

- Event or laboratory test abnormality, with plausible time relationship to drug intake
- Cannot be explained by disease or other drugs
- Response to withdrawal plausible (pharmacologically, pathologically)
- Event definitive pharmacologically or phenomenologically (i.e. an objective and specific medical disorder or a recognised pharmacological phenomenon)
- Re-challenge satisfactory, if necessary

Probable

- Event or laboratory test abnormality, with reasonable time relationship to drug intake
- Unlikely to be attributed to disease or other drugs
- Response to withdrawal clinically reasonable (for details refer to WHO-UMC)
- Re-challenge not required

Possible

- Event or laboratory test abnormality, with reasonable time relationship to drug intake
- Could also be explained by disease or other drugs
- Information on drug withdrawal may be lacking or unclear

Unlikely

- Event or laboratory test abnormality, with a time to drug intake that makes a relationship improbable (but not impossible)
- Disease or other drugs provide plausible explanations

Not related

The event does not follow a reasonable temporal sequence from administration of the IMP and is clearly related to other factors, such as clinical state, therapeutic intervention or concomitant therapy.

Not assessable

- Report suggesting an adverse reaction
- Cannot be judged because information is insufficient or contradictory
- Data cannot be supplemented or verified

All cases judged by any or both assessors as having a "reasonable causal relationship" to the IMP qualify as ADR. This corresponds to the categories "definite", "probable" and "possible".

10.6. Reporting of Serious Adverse Events

All Serious Adverse Reactions and all Unexpected Serious/Adverse Reactions with at least a suspicion of causal relationship to the investigational product must be reported. to the Sponsor within 24 hours (one working day) of the Investigator becoming first knowledge. Preference in the reporting is the SAE report by e-mail, however fax may be also used:

FSNN representative for pharmacovigilance reporting aspects:

[name] (contact details to be added)
Date: 040418

STUDY ID: CAPTAIN - rTMS

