13.5. ANALYSIS OF SAFETY

Safety analyses will be conducted on the ITT population and included the incidence of adverse events and serious adverse events.

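### A serious event that the site judges unrelated has no prompt route to the sponsor, although the sponsor's own causality judgement could make it a reaction

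*Protocol*

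**What the plan says.** **The 24-hour duty.** Protocol 10.6 is headed as covering serious adverse events, but its trigger is narrower: serious reactions and unexpected reactions "with at least a suspicion of causal relationship to the investigational product must be reported". The clock runs "to the Sponsor within 24 hours (one working day) of the Investigator becoming first knowledge". SAP 8.2.2 carries the same trigger and the same clock.

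**Other serious events.** Protocol 10.2.1 states: "Serious Adverse Events will due to the underlying constitution of the patient be considered for AE documentation". Only serious adverse drug reactions are then taken forward to the procedure that follows. SAP 8.2.2 repeats this.

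**Who judges causality.** Protocol 10.2 defines a reaction as a response "having a reasonable causal relationship as judged by either the Investigator or the Sponsor". Protocol 10.5.2 agrees: "All cases judged by any or both assessors as having a" reasonable causal relationship count as adverse drug reactions. It maps this to the categories definite, probable and possible.

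**What is analysed.** SAP 13.5 plans to report "the incidence of adverse events and serious adverse events".

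**The concern.** The protocol has two assessors of causality, and a positive view from either is enough. That protects patients only if the second assessor hears of the event. As written, prompt notice to the sponsor depends on a suspicion that already exists, and in practice this is the site's suspicion. The events on which the sponsor might disagree with the site are the ones not sent promptly.

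This matters more than usual here. There is one site, so no other investigator offers a comparison. Protocol 3.2 calls the study the first in TBI to test rTMS plus a drug for cognitive rehabilitation. Section 10.2.1 gives the patients' underlying condition as the reason for treating serious events as routine documentation, so attributing an event to the injury is foreseeable. The documents supplied describe no safety committee that would see such events by another path.

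**Working it through.** The plan gives no figure for this point, so the check is mainly a reading of the sections against each other, plus one day count.

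**1. The rules side by side**

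| Section | Rule | Consequence |
|---|---|---|
| Protocol 10.2, 10.5.2 | Investigator or sponsor; either suffices | The sponsor alone can make an event a reaction |
| Protocol 10.6, SAP 8.2.2 | 24-hour report if causality is suspected | Without suspicion, no 24-hour report |
| Protocol 10.2.1, SAP 8.2.2 | Other serious events go to AE documentation | Recorded, with no timed notice |
| Protocol 10.5 | All events go on the CRF; reported where applicable | No time limit |
| Protocol 10.7 | Not applicable | Adds no wider duty |

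**2. Whose suspicion counts.** Section 10.6 does not say. Two texts point to the site: the clock starts when the investigator learns of the event, and 10.2.1 describes causality "As judged by the reporting health care professional to have reasonable suspected causal relationship". This is an inference, but no text supports another reading.

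**3. Which events fall in the gap.** Serious events that the site classes as unlikely or not related under 10.5.2. Those classed as not assessable are unclear: they lie outside the three categories that make a reaction, yet their description starts from a report that suggests one.

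**4. Other routes to the sponsor.** There are two:
- Monitoring visits with source data verification (Protocol 15.2). They are regular, but the interval is not stated.
- Signed CRFs open to the clinical monitor within two weeks after each patient completes (Protocol 16.7.1). This is the only other route with a time limit.

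**5. Length of the delay by the timed route**

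Inputs: first treatment day 31 and last visit day 180 (Protocol 11.1); two weeks = 14 days (Protocol 16.7.1).

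Formula: longest wait = (last visit day - event day) + 14

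- Event on day 31: (180 - 31) + 14 = 149 + 14 = **163 days**
- Event on day 100, the last treatment day: (180 - 100) + 14 = 80 + 14 = **94 days**

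These are upper bounds if the patient completes on day 180 and the two-week limit is met. A monitoring visit could shorten them. The comparison is 24 hours for a suspected reaction.

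**The case against.** **The threshold for reporting is low.** At least a suspicion is enough, and under 10.5.2 an event can be possible, and so a reaction, even when disease or other drugs could explain it. Protocol 3.1 names seizures as the main area of concern with TMS in stroke or TBI, while noting that they have rarely been reported. A seizure with reasonable timing to treatment would fit the possible category and should trigger the 24-hour report. This stands. It makes the gap smaller but does not close it, because the remaining events are those on which the two assessors could differ.

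**The sponsor still sees the events.** The either-assessor rule carries no deadline, and monitoring and CRF review let the sponsor judge causality later. This also stands. A reader might infer that unrelated serious events never reach the sponsor, or that the two-assessor rule cannot operate at all. The documents support only delay.

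**Serious events would not be under-counted.** A reader might infer that the incidence planned in SAP 13.5 would miss events judged unrelated. That confuses fast notification with data capture. Protocol 10.5 and SAP 8.2.2 require every adverse event, serious or not, to be documented, and nothing says that the incidence is drawn from the 24-hour reports.

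**Seriousness is not confined to reactions.** The lead-in to the list in 10.2.1 names only an adverse drug reaction, so a reader might infer that an unrelated event cannot be serious. The section heading covers both events and reactions, and its closing note applies the idea of seriousness to both. The lead-in is loose wording. SAP 8.2.2 copies the list without that note, so an alignment is still worth making.

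**Conclusion.** The point holds as a conflict between the notification rule and the causality rule. Protocol 10.6, 10.2.1 and SAP 8.2.2 give the sponsor no prompt notice of serious events that the site considers unrelated, while Protocol 10.2 and 10.5.2 rely on the sponsor being able to judge them.

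The size is a delay of up to 163 days for an event on day 31 and up to 94 days for one on day 100, against 24 hours for a suspected reaction. This assumes that the suspicion in 10.6 is the site's, that completion means the day 180 visit, and that no monitoring visit finds the event first. The documents give neither a serious event rate nor the share likely to be judged unrelated, so the number of events affected cannot be stated.

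No loss of events and no bias in the planned serious adverse event incidence is shown. The matter is timely safety oversight, and the sponsor should correct it.

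**What to change.** 1. In Protocol 10.6 and SAP 8.2.2, require all serious adverse events, regardless of suspected causality, to be sent to the sponsor within the existing 24 hours.
2. Reconcile the AE-documentation sentence in Protocol 10.2.1, and its copy in SAP 8.2.2, with that duty.
3. As a wording alignment, change the lead-in of the seriousness list in both places to Adverse Event / Reaction, to match the note in Protocol 10.2.1.
4. Leave expedited onward reporting limited to events that are serious, unexpected and related.

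While 10.6 is open, settle the clock as well: 24 hours and one working day differ over a weekend or holiday.

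The cost is a wording amendment to both documents and a few more report forms from one site. No treatment, endpoint or analysis changes.

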10.7. Exemption from expedited reporting

not applicable

10.8. Adverse Event/Reaction follow-up procedures

Adverse Events/ Reactions will be followed up throughout the course of the clinical study and any changes will be recorded in the CRF.

11. STUDY SCHEDULE

11.1. Procedures at Each Visit

Screening and Baseline Visit – within 30 days of onset of TBI (Study Day 0)

- Neurological and physical exam
- Hematology and blood chemistry
- Demographic data
- Medical history
- Concomittant Medication
- Evaluation Scales
 - Processing Speed Index
 - Stroop Color-Word Test
 - Trail Making Test
 - Digit Span
 - Montreal Cognitive Assessment
 - Hamilton Anxiety Rating Scale
 - Hamilton Rating Scale for Depression
 - One Touch Stockings of Cambridge
 - Multitasking Test
 - Reaction Time
- ET

Date: 040418

STUDY ID: CAPTAIN - rTMS

Scales

Scales

qEEG

Treatment cycles

Each patient shall receive three cycles of treatment of 10 infusions on 10 consecutive days

- Study days 31-40,
- Study days 61-70
- Study days 91-100

Visit 1 – Efficacy Evaluation (study day 101)

- Neurological and Physical exam
- Evaluation
 - Processing Speed Index
 - Stroop Color-Word Test
 - Trail Making Test
 - Digit Span
 - Montreal Cognitive Assessment
 - Hamilton Anxiety Rating Scale
 - Hamilton Rating Scale for Depression
 - One Touch Stockings of Cambridge
 - Multitasking Test (MTT)
 - Reaction Time
- ET
- qEEG

Visit 2 – Efficacy Evaluation (study day 180)

- Neurological and Physical exam
- Evaluation
 - Processing Speed Index

Date: 040418

- Stroop Color-Word TestTrail Making Test
- Digit Span
- Montreal Cognitive Assessment (
- Hamilton Anxiety Rating Scale
- Hamilton Rating Scale for Depression
- One Touch Stockings of Cambridge
- Multitasking Test (MTT)
- Reaction Time
- ET
- qEEG

11.2. Assessment of Compliance

Compliance will be documented by recording the date and time of the administration in the CRF. The number of IV infusions/ rTMS sessions actually administered to each patient will be calculated as the percentage of the total number of IV infusions/rTMS sessions planned per protocol and will provide a measure of treatment compliance.

11.3. Risk assessment and Precautionary Measures

Both the investigational medicinal product and rTMS are in clinical use for many years and have demonstrated a very benign safety profile.

The safety information for the IMP is provided in the SmPC in Appendix 1.

Date: 040418

STUDY ID: CAPTAIN - rTMS

12. STUDY AND TREATMENT DURATION

Study/Treatment start: 04 / 2018

Study/Treatment end: 12 / 2020

13. STATISTICS

13.1. Statistical methods

The final statistical analysis of the study will be performed by a qualified biometrician and will fulfill all ICH/GCP requirements for handling of clinical study data. The statistical analysis, including any subgroup analysis will be agreed upon prior to data evaluation and the results will be fixed in a statistical analyses plan (SAP). The study data will be analysed and the Statistical Report written as soon as all study data are entered into the study data base and the entered data are validated.

13.2. Preliminary Remark

Although this study is intended to be of exploratory nature, the analysis will be based on 'confirmatory' principles with pre-specification of the primary analyses and control of multiple level alpha.

13.3. Primary Objective

It is the primary objective of this clinical study to assess the efficacy of the combining rTMS and Cerebrolysin treatment versus CRB alone, upon a battery of co-primary neurocognitive outcomes at 3 and 6 months post TBI.

13.4. Primary Efficacy Criteria

13.4.1. Justification for Multidimensional Approach

In the last 30 years, no TBI trial with a traditional design on neuroprotective agents showed a significant treatment effect in moderate to severe TBI (Maas, Roozenbeek, 2010). Thus, the challenge to demonstrate benefit of a novel treatment concepts in TBI is great, but the rewards are regarded as correspondingly high (Maas, Roozenbeek, 2010).

Almost all failed studies used a single measure approach. Nevertheless, outcome after TBI is by definition multidimensional, including neurophysical disabilities, disturbances in mental functioning (e.g., cognitive and executive functioning), and consequential problems in social reintegration.

Thus, in agreement with current recommendations, a multidimensional approach for outcome assessment and classification will be chosen for the present study.

An ensemble of appropriate single efficacy criteria shall be tested by a multivariate, directional test approach, reflecting the "global status of patients in TBI" (Bagiella, 2010), while simultaneously combining two points in time in the sense of a 'repeated measures design'.

13.4.2. Defined Efficacy Ensemble

The following ensemble of appropriate single efficacy criteria shall be tested by a multivariate, directional test approach, reflecting the global status of patients in TBI after 3 and 6 months:

Multivariate Efficacy Ensemble

- 1. Processing Speed Index, Changes from Baseline, LPCF, ITT
- 2. Stroop Color-Word Test, Changes from Baseline, LPCF, ITT
- 3. Trail Making Test, Changes from Baseline, LPCF, ITT
- 4. Digit Span, Changes from Baseline, LPCF, ITT
- 5. Montreal Cognitive Assessment, Changes from Baseline, LPCF, ITT
- 6. Stockings of Cambridge (CANTAB), Changes from Baseline, LPCF, ITT
- 7. Reaction Time (CANTAB) , Changes from Baseline, LPCF, ITT
- 8. Hamilton Rating Scale for Depression, Changes from Baseline, LPCF, ITT
- 9. Hamilton Anxiety Rating Scale, Changes from Baseline, LPCF, ITT

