13.9. Sample Size Calculation

The power for this study is determined based on the following design specifications:

- (a) One-sided type I error defined as alpha = 0.05 (multiple level alpha, see section 13.7)
- (b) Type II error defined as $\beta = 0.2$ (Testpower 80%)
- (c) Design alternative effect size: Mann-Whitney statistic (MW) = 0.64 (medium-sized difference according to Cohen (Colditz, 1988); assuming a normal distribution the effect size MW may easily be re-expressed as the well-known Cohen effect size (Cohen, 1988) of a standardized difference (Cohen's d): MW = 0.64 means Cohen's d = 0.5)
- (d) Estimated correlations among the single outcome scales included in the global statistics $\rho = 0.4$)

Nonparametric sample size calculations within the framework of a multiple outcome approach (Wei-Lachin procedure- Wei and Lachin, 1984; Lachin 1992) was performed applying the validated software Nnpar 1.0 from idv Data Analysis and Study Planning, Krailling/Munich (see also Tang, 1989; Lachin, 1981). A good example for sample size calculation according to the Lachin approach (Wei and Lachin, 1984; Lachin 1992; Lachin, 1981) in multidimensional trials with neuroprotective agents is also given by Huang (2008).

Please note: further details of the effect size (Mann-Whitney statistic) are described in section 13.10, further details of sample size assessment are described in the separate document "Sample Size Assessment Based on a Multidimensional Efficacy Approach".

Based on the above design specifications, the total required sample size for the multivariate ensemble results in 30 patients per group (including 10% enhancement for usual "ambiguities", e.g., dropouts). With this sample size a "medium-sized" group difference (MW = 0.64) with regard to the multivariate outcome ensemble at month 3 and 6 can be detected with a power of 80%.

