13.14. Homogeneity Analyses (Exploratory Interpretation)

Homogeneity analyses for baseline shall be performed based on the ITT population.

In addition to descriptive analyses robust nonparametric Mann-Whitney effects size measures and their two-sided 95% confidence intervals shall present an overview on demographic-anamnestic variables and on the primary efficacy criteria at baseline. This allows comparison of baseline variables across different scales and data types.

As benchmark for relevant baseline differences, a Mann-Whitney effects size measure of 0.36 and 0.64 respectively will be applied (referring to a standardized difference of 0.5 according to Cohen, which is regarded as a medium-sized difference).

In the case of heterogeneities, stratified analyses will be performed as second line analyses.

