9. SPECIFICATIONS OF EFFICACY CRITERIA

Multivariate Efficacy Ensemble

- 1. Processing Speed Index, Changes from Baseline, LPCF, ITT
- 2. Stroop Color-Word Test, Changes from Baseline, LPCF, ITT
- 3. Trail Making Test, Changes from Baseline, LPCF, ITT
- 4. Digit Span, Changes from Baseline, LPCF, ITT
- 5. Montreal Cognitive Assessment, Changes from Baseline, LPCF, ITT
- 6. Stockings of Cambridge (CANTAB), Changes from Baseline, LPCF, ITT
- 7. Reaction Time (CANTAB), Changes from Baseline, LPCF, ITT
- 8 Hamilton Rating Scale for Depression, Changes from Baseline, LPCF, ITT
- 9. Hamilton Anxiety Rating Scale, Changes from Baseline, LPCF, ITT

This ensemble of appropriate single efficacy criteria shall be tested by a multivariate, directional test approach, reflecting the global status of patients in TBI after 3 and 6 months.

All efficacy criteria will be analyze with descriptive group statistics.

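### The primary test ranks changes from baseline with no covariate adjustment beyond subtraction, which costs some power at moderate baseline correlation and favours whichever arm starts worse by chance

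*Protocol*

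**What the plan says.** - **Analysed quantity.** Protocol 13.4.2 lists nine scales, each as a change from baseline, for example "Processing Speed Index, Changes from Baseline, LPCF, ITT". SAP 9 has the same list, for example "Digit Span, Changes from Baseline, LPCF, ITT". Protocol 4.1.1 is looser and allows scores or score changes.
- **Test.** Protocol 13.10 uses a directional Wei-Lachin combination of Mann-Whitney statistics over both visits. SAP 12.2 (Confirmatory Statistics) names Kruskal-Wallis with Dunn's test and Bonferroni. Neither mentions a covariate, and Protocol 6.4 names no stratification factor for randomisation.
- **Baseline imbalance.** Protocol 13.14 flags a baseline Mann-Whitney value (MW) of 0.36 or 0.64. It then says: "In the case of heterogeneities, stratified analyses will be performed as second line analyses". The strata and the method are not given. The SAP has no counterpart.
- **Planning values (Protocol 13.9).** "One-sided type I error defined as alpha = 0.05"; 80% power; "Design alternative effect size: Mann-Whitney statistic (MW) = 0.64", with "MW = 0.64 means Cohen's d = 0.5"; "Estimated correlations among the single outcome scales included in the global statistics" of 0.4; and "30 patients per group (including 10% enhancement for usual" ambiguities such as dropouts.

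**The concern.** A change score is right for baseline only if follow-up moves one for one with baseline. When the slope is below 1, change is negatively correlated with baseline, and the arm that starts worse shows more apparent improvement without any treatment effect. Protocol 13.10 itself notes floor and ceiling effects, which tend to strengthen this. With 30 per arm and no stated stratification, chance gaps are to be expected.

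Two things are at stake: power that could be had from data already scheduled for every patient, and the credibility of a nominal 5% result if the baseline table shows the test arm starting worse. The flag in 13.14 sits at d = 0.5, the whole design effect, so smaller gaps draw no response.

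**Working it through.** **Inputs.** From Protocol 13.9: one-sided alpha 0.05, power 80%, MW 0.64 (d = 0.5), correlation between scales 0.4, 30 per group with a 10% allowance (30 × 0.9 = 27 evaluable). From 13.4.2: K = 9 scales. Assumed: baseline-to-follow-up correlation r (not in the documents), equal variances at baseline and follow-up, a linear relation, one visit, and the 0.4 applied to baselines as well.

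**1. The plan's own figure.** Noether's formula for one scale: (1.645 + 0.842)² / (12 × 0.25 × 0.14²) / 2 = 52.6 per group. The average of K equally correlated scales has variance factor (1 + 8 × 0.4)/9 = 0.467. So 52.6 × 0.467 = 24.5, rounded up to 25, and 25/0.9 gives 28. This is within two of the stated 30. Section 13.9 does not say which K was used.

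**2. Precision.** The variance of a change is 2s²(1−r); adjusted for baseline it is s²(1−r²). The ratio is (1+r)/2: 0.75, 0.85 and 0.95 at r = 0.5, 0.7 and 0.9. With 27 per arm and d = 0.5 on the change scale, SE = √(0.467 × 2/27) = 0.186 and 0.5/0.186 = 2.69.

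| Analysis | Calculation | Power |
|---|---|---|
| Change score | Φ(2.69 − 1.645) | 85% |
| Adjusted, r = 0.5 | Φ(2.69/√0.75 − 1.645) | 93% |
| Adjusted, r = 0.7 | Φ(2.69/√0.85 − 1.645) | 90% |
| Adjusted, r = 0.9 | Φ(2.69/√0.95 − 1.645) | 87% |

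These are linear-model values. Simulations of a Wei-Lachin test on rank residuals (nine scales, 0.4, 27 per arm, one visit) gave 79% rising to 85–87% at r = 0.5, 79–80% rising to 83–84% at r = 0.7, and no gain at r = 0.9. The base differs between simulations, but the gain is consistently about 8 to 4 points over r = 0.5 to 0.7.

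**3. False positives after a chance imbalance.** Let the test arm start worse by g standard errors on the nine-scale average. Under no effect, the change-score statistic has mean g√((1−r)/2) and SD √((1+r)/2). Over all randomisations the variances add to (1−r)/2 + (1+r)/2 = 1, so the overall error is 5%.

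A gap of at least 0.2 SD is 0.2/0.186 = 1.08 SE, which occurs in about 14% of trials. The mean g in that tail is about 1.59. At that value:
- r = 0.5: 1 − Φ((1.645 − 0.793)/0.866) = 16%
- r = 0.7: 1 − Φ((1.645 − 0.614)/0.922) = 13%

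Averaged over the whole tail these become 17% and 14%. Simulation gave 15–19% over r = 0.5 to 0.7, against 3–4% adjusted. With imbalance defined instead as an average baseline MW below 0.44, a second simulation gave 17% and 15% at r = 0.5 and 0.7, against 6–7% adjusted.

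**4. One scale against the ensemble.** A 0.4 SD gap on one scale with r = 0.6 biases that scale by (1 − 0.6) × 0.4 = 0.16 SD. Its share of a nine-scale average is 0.16/9 = 0.018 SD. Moving the average by 0.16 SD needs a mean gap of 0.4 SD over all nine. At 30 per arm its SE is √(0.467 × 2/30) = 0.176, so that is 2.27 SE, a chance of about 1.2% in the harmful direction.

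**5. The 13.14 flag.** At 30 per arm SE(MW) = √(61/(12 × 900)) = 0.0752 and 0.14/0.0752 = 1.86, so one scale is flagged by chance with probability 6.2%. Simulated with correlation 0.4, at least one of nine scales is flagged in about 35% of trials for the primary pair, and in about 66% over all three pairs.

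**The case against.** The strongest defence is that a pre-specified, unadjusted rank test of change is a legitimate choice. Protocol 13.2 calls the study exploratory in nature, and 13.10 deliberately prefers a method with few assumptions. This defence holds as to validity. A reader might infer several stronger faults that the documents do not support:

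- **That baseline is ignored.** It is not; a change score adjusts with slope 1. What is missing is adjustment beyond that.
- **That type I error is inflated or the sample size is wrong.** Step 3 shows that the overall error is held. MW 0.64 was set directly on the analysed scale, so the 30 per group is unaffected.
- **That adjustment always gains.** The ratio (1+r)/2 describes a linear model; the simulated rank version gained nothing at r = 0.9.
- **That a 0.4 SD gap costs a third of the design effect.** That compares the bias on one scale (0.16 SD) with the effect for the ensemble.
- **That the flag fires in 44% of trials or more.** 1 − (1 − 0.062)⁹ = 44% assumes independent scales, against the protocol's own 0.4.
- **That the flag contaminates the primary test.** Section 13.14 leads only to a second-line, exploratory analysis.

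What survives is the efficiency loss at moderate r and the conditional bias. Neither is answered by the exploratory label, because 13.2 also commits the analysis to confirmatory principles.

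**Conclusion.** The point holds as a matter of efficiency and conditional bias, and it should be addressed. For assumed r of 0.5 to 0.7 the plan gives up about 8 to 4 points of power. After an average baseline disadvantage of at least 0.2 SD in the test arm, its one-sided false-positive rate is about three times nominal (14 to 19%); adjustment keeps it at about 5% (3 to 7% over the simulations). At r near 0.9 the power gain disappears.

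The sizes rest on an assumed r, normal data, equal variances, a common correlation of 0.4 and a single visit. The direction of the bias needs only a follow-up-on-baseline slope below 1. Under the protocol the sole response to imbalance is an undefined second-line analysis; under the SAP there is none.

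**What to change.** 1. Reconcile the confirmatory test first: Wei-Lachin in Protocol 13.10, Kruskal-Wallis with Dunn's test in SAP 12.2. The adjustment has to be written for whichever test is kept.
2. Before unblinding, pre-specify a baseline-adjusted version for each scale and visit. If Wei-Lachin is kept, one form ranks the residuals of follow-up rank on baseline rank, pooled over arms, with covariates fixed in advance.
3. Specify a permutation or small-sample variance, since a simple residual-rank version ran slightly liberal in one simulation (5.5 to 6.0%).
4. Rank patients with missing-data code 2 below the lowest residual. Protocol 13.12.3 gives them the worst possible score, but once baseline is subtracted a patient with a poor baseline shows only a small decline, not the worst rank.
5. Keep the unadjusted change-score test as a sensitivity analysis, and replace the triggered stratification in 13.14 with descriptive reporting of baseline.

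**Cost.** No new data are needed, because every scale is already scheduled at baseline. Protocol 13.4.2, 13.10 and 13.14 and the matching SAP sections need new text. The Mann-Whitney effect would then refer to baseline-adjusted ranks, so it is less direct to explain, and the planning value of 0.64 no longer maps to it exactly. Pooling over arms also shrinks a real effect when baselines are imbalanced. If the blind has already been broken, report the adjusted analysis as a labelled sensitivity analysis.
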